10.0 Confidentiality, Privacy and Data Management

10.1 Confidentiality

10.1.1 Identifiers associated with data and/or specimens

Participant names, addresses, telephone/fax numbers, email addresses, date of birth, medical record numbers, social security numbers, etc. can be collected as part of this research study. All study data will be identified only by a code number rather than a name. The list linking the code number with any of the other identifiers is password protected and limited staff has access to it. Social security numbers are collected only for payment purposes and will not be stored after payment check is issued to the participant.

10.1.1.1 Use of Codes, Master List

All data will be identified only by a code number rather than a name. The list linking the code number to any other identifiers is stored in a password protected database, located on the Department of Psychiatry private network.

10.1.2 Storage of Data and/or Specimens

Paper files are stored in a locked filing cabinet in C5600D. Electronic data is stored on the Psychiatry server (Microsoft Server 2003) with active directory limiting access established by the Primary Investigator.

10.1.3 Access to Data and/or Specimens

Only the PI and 1-2 key research team members have access to the data/specimens.

10.1.4 Transferring Data and/or Specimens

N/A

10.2 Privacy

The research team has access only to information about the subjects provided by the subject during the research study. The Department of Psychiatry is extremely concerned about all issues related to privacy and confidentiality and is experienced in procedures of maintaining it effectively.

All study procedures including phone conversations, obtaining consent, and clinic visits will be conducted in private offices or exam rooms within the General Clinical Research Center. Participants are volunteers and may discontinue the research procedures at any time with no penalty or loss of benefits to which they are entitled.

11.0 Data and Safety Monitoring Plan

Although prazosin is routinely used in clinical settings in bulimic patients experiencing PTSD and nightmares and thus does not pose more than minimal risk for the patients, the research team will have the following data and safety monitoring plan to ensure safety and prevent any untoward outcomes.

11.1 Periodic evaluation of data

Subjects will be monitored weekly by a board certified psychiatrist to evaluate safety. The PI and co-investigators will be looking at the data monthly to further ensure safety of subjects.

11.2 Data that are reviewed

Vital signs, lab work, side effects and scales of symptom severity will be reviewed periodically to ensure safety.

11.3 Method of collection of safety information

The information will be collected at study visits and if needed, follow up phone calls will also be used.

11.4 Frequency of data collection

Data collection will be as described in the methods and recruitment section. Vital signs will be collected at every visit; similarly adverse events will be monitored on a weekly basis. Scales of symptom severity will be collected 4 times during the duration of the study.

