7.2.3 Weekly Visits

Symptoms will be reassessed and medication will be adjusted by 1-2 mg increments every 7 days based on clinical response and severity of night mares, to achieve maximum therapeutic benefit while monitoring adverse effects using side effects scale on weekly basis (psychiatrist will be using the scale at every visit). A phone contact by RA will be made on the morning after dose initiation and after each increment to monitor adverse events. The end point for capping the Prazosin dose will be 6 mg daily. The psychiatrist will administer adverse events rating scale and nightmare assessment using Sleep-50 Questionnaire at every psychopharmacologic

visit after initiation of medication in addition to the initial visit. Vital signs will be checked at each visit as well. The participants will have a total of 7 visits with the psychiatrist (1 for initial evaluation and 3 for the dose titration during each study arm). Research pharmacy and RA will determine and track the sequence and random allocation of the medication to ensure blind randomized trial. RA will also gather salivary samples from the patient at end of each study arm (5 diurnal samples for each arm) After 3 weeks on one treatment arm, a wash out period of 1 week will be given prior to starting the second study arm. The same sequence will be repeated for the second study arm and study questionnaires will be repeated on the last day of the washout period. Blood work will be drawn thrice, once at baseline and once at the end of each study arm. 5 Diurnal salivary samples will be collected thrice, once at baseline and once at the end of each study arm. All sets of cortisol level will be collected at the same time points as the baseline level to allow accurate comparisons. All Rating scales will be completed 4 times, once at baseline, once at end of wash out period and once at the end of each study arm. At the end of each study arm, any unused medication will be collected from the participant. Upon completion of the study, participants may want to continue taking the study medication if they experienced positive results. The PI will discuss with each participant if it is appropriate to continue taking the medication.

Study Procedures (PHASE B)

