7.3 Duration of Participation

The study duration is 7 weeks.

Phase A (No PSG Recordings)

		Day 1	Day 2	Day 3	Day 4	Day 5	Day 6	Day 7
Screening	Consent	x						
	Blood Collection, Urine Pregnancy Test, &EKG	x						
	Standard Evaluation by Therapist	x						
Baseline Procedures	Psychiatric Assessment & Randomization		x					
	Saliva Collection (8a, 12p, 3p, 6p, 9p)		x					
	Rating Scales (RS) and Vitals		x					
	Start Treatment		x					
Intervention Arm 1	Week 1	Psychiatrist Visit	x					
		Vitals, Adverse Event Rating Scale (AERS), Sleep-50	x					
		Research Assistant Phone Call		x				
	Week 2	Psychiatrist Visit	x					

		Vitals, AERS, Sleep-50	x						
		Research Assistant Phone Call		x					
	Week 3	Psychiatrist Visit	x						
		Vitals, AERS, Sleep-50	x						
		Research Assistant Phone Call		x					
		Saliva/Blood Collection & RS							x
Washout	Week 4	Rating Scales							x
Intervention Arm 2	Week 5	Psychiatrist Visit	x						
		Vitals, AERS, Sleep-50	x						
		Research Assistant Phone Call		x					
	Week 6	Psychiatrist Visit	x						
		Vitals, AERS, Sleep-50	x						
		Research Assistant Phone Call		x					
	Week 7	Psychiatrist Visit	x						
		Vitals, AERS, Sleep-50	x						
		Research Assistant Phone Call		x					
		Saliva/Blood Collection & RS							x

Phase B (2 subjects have PSG Recordings)

			Day 1	Day 2	Day 3	Day 4	Day 5	Day 6	Day 7
Screening	Consent		x						
	Blood Collection, Urine Pregnancy Test, &EKG		x						
	PSG Recording				x				
	Standard Evaluation by Therapist		x						
Baseline Procedures	Psychiatric Assessment & Randomization			x					
	Saliva Collection (8a, 12p, 3p, 6p, 9p)			x					
	Rating Scales (RS) and Vitals			x					
	PSG Recordings					x	x		
	Start Treatment							x	
Intervention Arm 1	Week 1	Psychiatrist Visit	x						
		Vitals, AERS, Sleep-50	x						
		Research Assistant Phone Call		x					
	Week 2	Psychiatrist Visit	x						
		Vitals, AERS, Sleep-50	x						
		Research Assistant Phone Call		x					
	Week 3	Psychiatrist Visit	x						
		Vitals, AERS, Sleep-50	x						
		Research Assistant Phone Call		x					
		Saliva/Blood Collection & RS							x
		PSG Recordings					x	x	x
Washout	Week 4	Rating Scales							x
Intervention Arm 2	Week 5	Psychiatrist Visit	x						

		Vitals, AERS, Sleep-50	x						
		Research Assistant Phone Call		x					
Week 6		Psychiatrist Visit	x						
		Vitals, AERS, Sleep-50	x						
		Research Assistant Phone Call		x					
Week 7		Psychiatrist Visit	x						
		Vitals, AERS, Sleep-50	x						
		Research Assistant Phone Call		x					

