24.1.4 Subject Compliance Monitoring

Subjects will be seen by the psychiatrist each week during the study duration and will be asked to bring along their pill bottle so any remaining capsules can be counted and collected. The research assistant will also call the participants after each dosage increase to inquire about usage and side effects.

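### Adverse events are to be rated weekly, but neither schedule has a rating after the last week of either arm, and no rule assigns events to a treatment period

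*Combined protocol and SAP*

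**What the plan says.** Four parts of the combined protocol and SAP bear on this.

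- **Promised frequency.** Section 11.4: "similarly adverse events will be monitored on a weekly basis". Section 7.2.3 describes "monitoring adverse effects using side effects scale on weekly basis (psychiatrist will be using the scale at every visit", and has the psychiatrist give the scale and Sleep-50 at every "visit after initiation of medication in addition to the initial visit". Section 24.1.4 adds: "Subjects will be seen by the psychiatrist each week during the study duration".
- **Number of psychiatrist visits.** Section 7.2.3: "The participants will have a total of 7 visits with the psychiatrist (1 for initial evaluation and 3 for the dose titration during each study", that is, three per treatment period.
- **Schedules (section 7.3, Phases A and B).** The row "Vitals, Adverse Event Rating Scale (AERS), Sleep-50" (abbreviated after its first use) is marked on Day 1 of Weeks 1, 2 and 3 under Intervention Arm 1 and of Weeks 5, 6 and 7 under Intervention Arm 2. Day 7 of Weeks 3 and 7 carries "Saliva/Blood Collection & RS", plus polysomnography in Phase B. Week 4 carries rating scales only, on Day 7. The subjective scales listed in section 7.2 do not include AERS.
- **Other contact.** Section 7.2.3: "A phone contact by RA will be made on the morning after dose initiation and after each increment to monitor adverse events". The schedules mark this call on Day 2 of each treatment week.

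Section 9.2 contains no adverse-event analysis, section 11.7 marks statistical tests as not applicable, and no section gives a look-back window for AERS or a rule for assigning an event to a treatment period.

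**The concern.** In a crossover with weekly upward titration, the last week of each arm follows the last opportunity to change the dose. A scale given only at the start of each week describes the week before, so the last week is described only if a further rating follows it. The schedules provide none within the arm. After arm 1 the next rating comes once washout is over and stands under the heading of the other treatment. After arm 2 no rating follows at all.

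At stake is the completeness of the structured safety record for the period after the last titration visit, and whether an event reported at Week 5 Day 1 can be tied to the right treatment. In patients who receive prazosin second, the unrated week also comes just before the investigator discusses whether to continue the drug (section 7.2.3). With 8 to 10 patients, each lost or misplaced event counts.

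**Working it through.** **Inputs.** AERS days, call days and Day 7 procedures come from section 7.3; arms of 3 weeks with 1 week of washout from section 7.1; bedtime dosing from section 24.1.2. Days are numbered from Week 1 Day 1, so Week w Day k is day 7(w − 1) + k.

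**The plan's own counts reproduce.**
- Psychiatrist visits: 1 initial + Day 1 of six treatment weeks = 7, as section 7.2.3 states.
- Rating-scale occasions: baseline, Week 3 Day 7, Week 4 Day 7 and Week 7 Day 7 = 4, as sections 7.2.2 and 11.4 state.

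The stated total of 7 therefore leaves no psychiatrist visit for Day 7 of Week 3, 4 or 7.

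**Spacing of AERS.** The days are 1, 8, 15, 29, 36 and 43. The gaps are 7, 7, 14, 7 and 7 days. From the last AERS to the end of arm 2 is 49 − 43 = 6 days with no further rating.

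**Dosing nights followed by an AERS in the same arm** (a rating on day d covers nights before d):
- Arm 1, nights 1 to 21, last AERS on day 15: 14 nights covered, nights 15 to 21 not, so 7 of 21.
- Arm 2, nights 29 to 49, last AERS on day 43: 14 nights covered, nights 43 to 49 not, so 7 of 21.

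**Counting the Day 2 call as an adverse-event contact.** The last calls fall on days 16 and 44. Nights 16 to 21 and 44 to 49 remain, 6 of 21 in each arm. This is the favourable count: the text ties calls to initiation and increments, so a week without an increment might have none.

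**Week 5 Day 1.** Bedtime dosing, and a Day 2 call described as the morning after initiation, imply that this AERS precedes the first arm-2 capsule. That is an inference. Section 7.2.2 also allows divided dosing, which does not agree with section 24.1.2.

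**With AERS added on days 21 and 49.** Covered nights rise from 14 to 20 of 21 in each arm, on days that already have procedures.

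**A loose end in arm 1.** The Phase A schedule starts treatment on baseline Day 2 and then shows a separate Week 1 Day 1 visit, so arm 1 may not be exactly 21 nights. The gap in its last week is unaffected.

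**The case against.** The strongest reply is that no planned analysis is harmed. No endpoint in sections 1.2 to 1.5 is an adverse event, section 9.2 compares none, and the data serve patient monitoring. This stands, and it rules out any claim that a planned comparison is biased.

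A reader might still infer that the schedule credits prazosin harms to placebo and shrinks the observed difference. The documents do not support this. It would need the prazosin-first sequence, a look-back reaching past the one-week washout, and filing by schedule heading; neither of the last two is stated. In the placebo-first sequence, late placebo events could equally be listed under prazosin. Nor can a size be given. Suppose constant weekly rates p on prazosin and q otherwise, equal sequences and filing by heading. The true three-week excess is 3(p − q). With look-back to the last rating, the average recorded is 2p + q on prazosin and 0.5p + 2.5q on placebo, an excess of 1.5(p − q), or half. With a 7-day look-back it is 2p + 0.5q and 2.5q, an excess of 2(p − q), or two thirds, and no prazosin event is credited to placebo. The answer follows from the assumptions.

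It can also be said that other contacts fill the gap. Section 11.3 collects safety information at study visits, with calls if needed; bloods are drawn at the end of each arm; and section 7.2 repeats baseline procedures on completion. So it would be too strong to say that last-week events are certain to be lost: what is missing is the structured rating. But section 11.3 assigns no AERS to Day 7. The repeat of baseline procedures does not name the scale, and it includes sleep recordings that Phase A lacks, so it is not a dependable schedule. The weekly psychiatrist contact in section 24.1.4 would need a washout visit that neither the schedules nor the count of 7 contains.

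Finally, adding a scale on Day 7 is not quite free, because the psychiatrist gives AERS while the research assistant collects the Day 7 scales. This stands and shapes the fix.

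**Conclusion.** The text promises weekly rating and the schedules do not deliver it. About 7 of 21 dosing nights per arm (6 of 21 with the Day 2 call) have no later scheduled adverse-event rating in that arm. The interval across washout is 14 days, and nothing follows Week 7 Day 1. Last-week events may be missed by the scale, or assigned to the wrong period if anyone groups them by schedule heading.

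The counts assume bedtime dosing and 21 nights per arm; divided dosing or an arm-1 lead-in would move them slightly without closing the gap. The direction and size of any bias in a treatment comparison remain undetermined. A pre-dose reading at Week 5 Day 1 is not in itself an error, and it does not touch the primary measure, the CAPS distressing-dream item collected at the end of each arm. This is a cheap improvement to the safety record, not a threat to the efficacy analysis.

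**What to change.** 1. In both schedules in section 7.3, add AERS to the Day 7 procedures of Weeks 3 and 7, and optionally to Week 4 Day 7. Ask about events since the last rating, with onset dates.
2. State who rates. Section 7.2.3 has the research assistant help to determine and track the allocation, so the rater should be someone blind to it: for example, a participant-completed form reviewed by the psychiatrist, or a brief psychiatrist contact. If psychiatrist contacts are added, amend the stated total of 7 visits.
3. In section 9.2, state that any by-treatment summary attributes events by onset date to the treatment being taken, and that the Week 5 Day 1 AERS and Sleep-50 are start-of-period readings. This rule alone is not enough, because the last week of arm 2 would still have no rating to attribute.
4. Reconcile sections 7.2.3, 11.4 and 24.1.4 with the schedules, and reconcile the dosing-time statements in sections 7.2.2 and 24.1.2.

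The cost is a short amendment, a few more minutes at two or three existing visits per patient, and a little rater time. No new visit day is needed.

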11.5 Individual's reviewing the data

The data will be reviewed by PI and co-investigators, the findings will be reported to the IRB by PI.

11.6 Frequency of review of cumulative data

Monthly reviews of the data will be conducted

11.7 Statistical tests

N/A

11.8 Suspension of research

Any life threatening adverse events or outcomes endangering subject safety will trigger immediate suspension of research.

12.0 Risks

There may be discomfort associated with removing blood by venipuncture (by needle from a vein). A slight pinch or pin prick may be felt when the sterile needle enters the skin. The risks include mild discomfort and/or a black and blue mark at the site of puncture. Less common risks include a small blood clot, infection or bleeding at the puncture site, and on rare occasions fainting during the procedure.

There is no risk involved with the collection of saliva for diurnal cortisol testing.

There is a minimal risk associated with the discomfort of having standard clinical EEG paste electrodes applied to the scalp and EKG Stickers applied to the chest when performing polysomnography. Rarely, we have had an individual who has had a mild allergic reaction to the tape applied over electrodes. This risk is minimized by using hypoallergenic tape. If a sleep disorder is discovered, the participant will be referred to a sleep specialist or family doctor for further follow up as needed.

There is no risk or real discomfort associated with an EKG, however body hair can sometimes interfere with the signal recording and at times a small patch of hair may need to be shaved in order to place the electrode. Abnormal findings will be reviewed by a physician and referred to cardiologist for further follow up, if needed.

There is a risk of loss of confidentiality if medical information or identity is obtained by someone other than the investigators, but precautions will be taken to prevent this from happening.

The most common side effect of low-dose Prazosin when administered at bedtime may cause orthostatic hypotension especially after first dose. Other common side effects of Prazosin include palpitations, headache, dry mouth, blurred vision, dizziness, fatigue, constipation, diarrhea and nausea.

The risks to an unborn baby or a nursing child from the study drug are largely unknown, though some animal studies suggest adverse events. Limited use in pregnant women has not demonstrated any fetal abnormalities or adverse events. Women who are pregnant or are nursing a child may not participate in this research study. Participant must agree to take reasonable and necessary precautions against becoming pregnant during the period of the investigation. The investigator will discuss appropriate precautions with participant. If at any point during the research participant believes there is any possibility of pregnancy, they must notify the investigator immediately.

When participants are in the group that receives placebo, their condition will go without active treatment for three weeks in addition to the one-week washout period and their symptoms may get worse.

13.0 Potential Benefits to Subjects and Others

13.1 Potential Benefits to Subjects

The subjects will have no direct benefits. During the active treatment arm, symptoms may get better.

13.2 Potential Benefits to Others

There is no previous study demonstrating the benefits of the Prazosin use in Bulimic patients for treatment of night mares related to PTSD. This project will provide insight into the effectiveness of this medication and aims to decrease the distress associated with nightmares.

14.0 Sharing Results with Subjects

The individual results will not be shared with the subjects or their healthcare providers. If a condition is discovered, the participant will be referred to their family physician for appropriate follow up care.

15.0 Economic Burden to Subjects

15.1 Costs

N/A

15.2 Compensation for research-related injury

The research involves no more than minimal risk to subjects that they may incur as part of routine treatment with Prazosin. It is the policy of the institution to provide neither financial compensation nor free medical treatment for research-related injury. In the event of injury resulting from this research, medical treatment is available but will be provided at the usual charge. Costs for the treatment of research-related injuries will be charged to subjects or their insurance carriers.

16.0 Number of Subjects

Subjects: 15 patients will be identified and screened for participation in the study. Only 10 patients with Bulimia nervosa and PTSD will complete the study and be included in the final analysis. The additional 5 participants will allow for screen failures or participant withdrawal after consent is obtained. This sample size has been derived from the previous studies in PTSD that have investigated the role of Prazosin in alleviating nightmares and other PTSD symptoms.

17.0 Resources Available

17.1 Facilities and locations

Briarcrest Clinic & GCRC– For recruitment and enrollment as well as follow up with psychiatrist to monitor symptoms.

17.2 Feasibility of recruiting the required number of subjects

The potential subjects are the patients who already follow up with the eating disorders clinic; the therapist will screen all patients following up with her for potential suitability to participate in the study until the proposed number of subjects has been recruited.

17.3 PI Time devoted to conducting the research

PI will devote 10% of time to this project to ensure that it is completed in the projected time frame. 1% of this time will be unfunded effort supported by Psychiatry.

17.4 Availability of medical or psychological resources

A therapist will be available for the assessment and screening as well as providing routine support for any ongoing issues. A referral to cardiologist will be made for any patients where cardiac assessment is indicated to ensure the cardiac stability of these patients.

17.5 Process for informing Study Team

The PI will meet with each team member separately to inform them of their expected participation and duties. The PI will also send a copy of the written protocol after IRB approval to each team member to ensure accurate understanding of procedures and will be available to answer questions by the research team.

18.0 Other Approvals

Approval from the departmental review committee and GCRC advisory committee will be obtained.

19.0 Subject Stipend (Compensation) and/or Travel Reimbursements

Subjects will be paid \$500 for participation in the 7 week study. The 2 subjects who also participate in phase 2 (Protocol B) will receive an additional \$500.

20.0 Multi-Site Research

20.1 Communication Plans

N/A

